Male	0.15	2.8	1.8	1.5	43.7	0	48.5
Total	0.3	5.6	3.6	3.0	87.5	0	100.0

Research Materials: We will be obtaining blood samples to measure hormone and glucose concentrations.

Recruitment of Subjects: Subjects will be recruited using IRB-approved advertising. Eligible subjects who express interest in participating in the study will be invited to the CRTU for a screening visit.

The following are exclusion criteria:

- Age <18 or >40
- BMI < 19 or > 28 kg/m²
- Medication that can affect glucose metabolism (determined by PI)
- Any chronic illness
- Upper GI surgery
- History of diabetes
- FBG >100 mg/dL
- For female subjects a positive pregnancy test

Potential Risks: Blood sampling. Blood samples are collected by venipuncture for this study. Bruising can occur with venipuncture, as can fainting, etc. Risk Monitoring / Risk Reduction: The samples are collected using aseptic technique in designated venipuncture areas of the CRTU where facilities are available should untoward reactions (fainting, etc.) occur. Given the aseptic nature of the sample collection and the small risk of bruising, the monitoring plan is focused on advising volunteers to call the investigators should they have unusual pain or discomfort from the venipuncture site. Blood drawn within a 12 week period will not exceed 550mL (one pint).

Vascular catheter placement. Catheter insertion, intravenous infusion and blood withdrawal are associated with a small risk of phlebitis. Risk Monitoring / Risk Reduction: This will be minimized by careful attention to sterile technique. If phlebitis occurs, it will be treated conservatively with heat and when appropriate, with antibiotics. The catheters will be cared for by experienced CRTU nurses in order to minimize the risk of these complications. In all protocols, “arterialized – venous” blood will be obtained by placing a hand in which a catheter has been inserted in a heated box during the study. The temperature inside the box is maintained at ~55°C. With prolonged exposure to continuous heat, there is a potential risk of local skin irritation or a minor burn. If this occurs, it will be treated appropriately. Catheter risks will be discussed with the volunteers prior to obtaining consent for the study.

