Radiation. Subjects will be exposed to radiation in this study. Radioactive tracers will be used in the proposed studies. Lean body mass and percent body fat will be measured at the time of screening using DEXA (dual energy x-ray absorptiometry). Risk Monitoring / Risk Reduction: The lowest dose of radioactive tracers that can be reliably counted in plasma will be used. In all instances, the amount of radiation that a volunteer will receive will be well below levels that result in significant risk of harmful effects. Proposed radiation exposure will be reviewed by the Mayo Clinic Radiation Safety Board prior to initiation of any study. Women who could become pregnant will be required to have a negative pregnancy test prior to participation in each study utilizing radioactive tracers. The Mayo CRTU body composition core has a QDR4500 with fan scan technology which allows body composition to be performed in only a few minutes.

Deuterated Water. Deuterated water will be given in 3 divided doses at 2200, 2400 and 0200. Risk Monitoring / Risk Reduction: Deuterated water is sometimes associated with dizziness and vertigo which is reduced by giving the tracer in divided doses. The fact that it is given late at night while the patient is in bed will reduce the risk of falls. Prior experiments using deuterated water have suggested that the occurrence of this uncommon.

Infusion of Tracers, Hormones. All infusions carry a risk of allergic reactions, bruising, discomfort at the site of infusion, and infection. Risk Monitoring / Risk Reduction: All infusates are prepared by trained personnel (under the supervision of a research pharmacist) in a laminar flow cabinet using aseptic technique. Infusions take place on the CRTU where facilities are available should untoward reactions occur. Somatostatin infusion will be undertaken under the auspices of an IND obtained from the FDA. Somatostatin use can be associated with nausea and hypotension. In prior experience these effects are minor and disappear within minutes of cessation of somatostatin infusion. Insulin can lower the levels of glucose in the blood and cause symptoms of hypoglycemia. Plasma glucose will be monitored at regular intervals during study visits. Vital signs will be monitored hourly as per our standard practice during infusions in the CRTU.

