Confidentiality. All studies expose participants to the psychosocial risks arising from any breach in confidentiality. The risks include anxiety, confusion, damage to family relationships or a compromised ability to obtain insurance or employment. These risks may not be confined to the individual but may extend to other family members. Risk Monitoring/Risk Reduction: The nature of the information obtained will be explained in detail to each participant. All information will be stored anonymously in the database and only the PI or one of his designates will have access to the data.

Data Safety and Monitoring Plan. The ultimate goal of this application is to further our understanding the role of different therapies in the management of diabetes. The DSMP utilized will adhere to the protocol approved by the Mayo Clinic IRB. We propose the following plan: -

Data quality and management: The principal investigator will review all data collection forms on an three-monthly basis for completeness and accuracy of the data as well as protocol compliance.

Adverse events grading: The common grading scale listed below will be used to grade AEs:

- 0 No adverse event or within normal limits or not clinical significant
- 1 Mild AE, did not require treatment
- 2 Moderate AE, resolved with treatment
- 3 Severe AE, resulted in inability to carry on normal activities and required professional medical attention
- 4 Life threatening or disabling AE
- 5 Fatal AE

Attribution scale: An adverse event includes both, an expected side effect that is of a serious nature, or an unexpected side effect/ event regardless of severity. All events will be graded as to their attribution (unrelated to protocol, or possibly, probably, or definitely related to protocol). Any event that is reported to either the principal investigator or his designated research associates by the subject or medical staff caring for the subject and which meets the criteria will be documented as such.

Data Monitoring. The majority of data generated from these protocols will be from analyses performed in our laboratory or the immunochemical core laboratory. Standard quality control procedures are in place for each assay. Genotyping results are examined for consistency between repeated genotypes of a given sample chosen at random. The frequency of data review for this study differs according to the type of data and can be summarized in the following table:

Data type	Frequency of review

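### Expected effects count as adverse events only if serious, so the non-serious effects the protocol predicts need not be documented and the weekly adverse event rates would run low

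*Combined protocol and SAP*

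**What the plan says.** All the relevant text is in section E (Human Subjects) of the combined protocol and SAP.

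- **Definition** (in the Attribution scale paragraph of the Data Safety and Monitoring Plan): "An adverse event includes both, an expected side effect that is of a serious nature, or an unexpected side effect/ event regardless of severity".
- **Documentation rule** (same paragraph): an event reported to the principal investigator or designated research associates, by the subject or by treating staff, "which meets the criteria will be documented as such".
- **Grading** (Adverse events grading): a scale from 0 to 5, in which grade 1 is "Mild AE, did not require treatment" and grade 2 is a moderate event that resolved with treatment.
- **Review** (table under Data Monitoring): adverse event and safety rates are looked at weekly.
- **Risks named in advance** (Potential Risks and the paragraphs after it). For somatostatin: "Somatostatin use can be associated with nausea and hypotension", followed by "In prior experience these effects are minor and disappear within minutes of cessation of somatostatin infusion". For insulin: "Insulin can lower the levels of glucose in the blood and cause symptoms of hypoglycemia". For the water tracer: "Deuterated water is sometimes associated with dizziness and vertigo". For the lines: "Catheter insertion, intravenous infusion and blood withdrawal are associated with a small risk of phlebitis". The blood sampling paragraph adds bruising and fainting, and the catheter paragraph adds skin irritation or a minor burn from the heated box.

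**The concern.** Whether an effect was expected, and whether it was serious, normally decide how far and how fast an event is reported onward. Here they decide whether it is an adverse event at all. The subjects are healthy volunteers undergoing infusions, catheters, a heated box and an oral tracer. The events most likely to occur are those the protocol has already listed, in mild form, and the definition leaves these out unless they are serious.

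What is at stake is the safety record. A weekly rate built on this definition can look clean while nausea, dizziness, phlebitis or minor burns are occurring. Any later safety summary drawn from the same record would have the same gap.

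**Working it through.** The plan gives no adverse event rate, so there is no figure to reproduce. The check is to apply the definition to each listed risk.

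**Step 1: the two limbs.** An event qualifies if it is (a) expected and serious, or (b) unexpected, at any severity. An event that is expected and not serious satisfies neither.

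**Step 2: which effects are expected.** The protocol does not define the term. The natural reading is that a risk the protocol itself lists is an expected one.

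**Step 3: apply the limbs to the non-serious form, and look for any other stated route into the record.**

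| Effect | Paragraph in section E | Limb (a) | Limb (b) | Other stated capture |
|---|---|---|---|---|
| Bruising, fainting | Blood sampling | fails | fails | None that documents it; volunteers are told to call about unusual pain or discomfort at the site, but a call is only a report |
| Phlebitis | Vascular catheter placement | fails | fails | None |
| Skin irritation, minor burn | Vascular catheter placement | fails | fails | None |
| Dizziness, vertigo | Deuterated Water | fails | fails | None |
| Nausea | Infusion of Tracers, Hormones | fails | fails | None |
| Hypotension | Infusion of Tracers, Hormones | fails | fails | Partial: hourly vital signs during infusions |
| Hypoglycemia symptoms | Infusion of Tracers, Hormones | fails | fails | Partial: glucose every 10 minutes during the clamp (section C), which captures the value but not the symptom |

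The protocol's own description of the somatostatin effects as minor and short-lived puts their usual form on the non-serious side.

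**Step 4: follow the result through the system.** The documentation rule passes on only events that meet the definition. The grading scale is for adverse events, so it applies to what has already qualified. The weekly review then sees adverse event rates from which the effects in Step 3 may be absent. No rule converts an abnormal vital sign or glucose reading into an adverse event.

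**Step 5: exposure.** Planned study days = 15 subjects × 2 days = 30. If a share *p* of those days carried a non-serious listed effect, up to 30 × *p* affected days could go without an adverse event entry. The documents give no value for *p*, so only the direction of the error is established.

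**The case against.** The best case for the present text has five parts.

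1. **The verb is *includes*, which need not be exhaustive.** This does not rescue the text. Documentation depends on meeting the criteria, and this definition is the only criterion given. At best the paragraph is ambiguous.
2. **Mild and moderate grades exist, so mild events must be in scope.** A reader might go further and infer that the scale contradicts the definition. Neither inference holds. Unexpected events qualify at any severity, so the low grades have a proper use. The definition is too narrow; it is not in conflict with the scale.
3. **Other monitoring exists.** This stands in part. The paragraph governs what is documented as an adverse event and does not forbid other recording. Hypotension and low glucose would leave a trace in the vital signs and glucose data, and study data are also reviewed weekly. It would therefore be wrong to infer that these effects go unrecorded altogether. The point does not extend to nausea, dizziness, phlebitis or a minor burn. The review table also mentions safety rates and injuries, but names no separate source for them.
4. **Neither *expected* nor *serious* is defined, and seriousness is not tied to a grade.** This stands as a limit. An investigator could class some treated events, such as phlebitis given antibiotics, as serious. The text therefore does not support saying that every expected grade 1 or 2 event is excluded, only that every non-serious one may be.
5. **The monitoring plan is to follow the IRB-approved protocol.** It says so, but no wider definition appears in these documents. Institutional rules cannot be seen from here, in either direction.

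**Conclusion.** The point holds as a defect in the safety-recording rule. Non-serious forms of the listed effects need not be documented as adverse events, and the weekly rates would understate the likeliest procedure-related events. This follows from a rule the protocol states, not from missing detail. The bias is downward, over 30 planned study days, and its size is unknown.

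It rests on two assumptions: that the listed risks count as expected, and that the definition is the whole of the criteria the documentation rule refers to. Both are the natural reading.

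Two larger conclusions might be inferred and are not supported. One is that the rule would conceal an excess of events on the 0.8 mU/kg/min insulin day. No comparison of adverse events by study day is planned. Somatostatin, the water tracer, catheters and the heated box are common to both days, and low glucose values are measured on both. The other is that the trial's results are affected. The EGP hypotheses and their analyses do not use adverse event data.

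The text should be corrected because the gap concerns the effects most likely to occur and the correction is cheap.

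**What to change.** In the Attribution scale paragraph of section E, define an adverse event as any untoward occurrence during participation, regardless of expectedness or severity. Record five separate fields for each event: grade, seriousness, expectedness, attribution and study day (0.4 or 0.8 insulin). Say what counts as serious, and state that the risks listed in section E are the expected effects.

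If the present wording is kept, use it only as a threshold for further reporting, and say to whom; the documents do not now give it that role. The investigators should also state when a vital-sign or glucose reading is to be entered as an event. That criterion is theirs to set.

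The cost is an amendment to one paragraph and slightly more event recording by existing CRTU staff. No visit, sample or analysis changes.
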